10.5.2. Analysis of safety

A safety analysis based on the total safety cohort will include all subjects who were vaccinated as per Korean PI and have completed 21-days follow-up after at least one dose, regardless of the number of dose.

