 - Recording of SAEs from the date of vaccination until 21 days (Day 0 to Day 20) after *Fluarix Tetra* is administered during the subject's participation in the study.
 - All AEs , ADRs and SAEs starting immediately following administration of *Fluarix Tetra* must be recorded onto the CRF and all ADRs and SAEs must be reported using the ADR reporting form and SAE reporting form, the latter to be sent to GSK according to the required timelines, irrespective of intensity or whether or not they are considered vaccination-related.
 - Parents of children aged 6 months to <12 years wil be contacted to provide details of any AEs experienced by the children 21 days after the children receives the vaccination.
 - Subjects for whom diary card transcription into CRF will be done through phone contact are considered to have completed the drug use investigation.
- Blood Samples: No blood samples will be collected in this drug use investigation.
- All subjects who receive at least one dose of the *Fluarix Tetra* and can be evaluated for whether the subject experienced an AE will be included in the safety population. For each subject, this drug use investigation will include a single or two visits and a follow-up contact 21 days (Day 0 to Day 20) after each vaccination with *Fluarix Tetra*.
- Pregnant subjects who receive *Fluarix Tetra* or subjects who become pregnant within 21 days after vaccination with *Fluarix Tetra* will be followed to determine the outcome of the pregnancy, if possible. At the end of the pregnancy, whether that be full-term or premature, information on the status of the mother and child will be forwarded to GSK, if possible. Generally, follow-up should be no longer than 6 to 8 weeks following the EDD, if possible.
- Duration of the drug use investigation:
 - 6 years (for children 36 months and above and adults).
 - 4 years (for children from 6 to 35 months of age)
- Type of drug use investigation: Self-contained.

- Data collection: Standardised hard copy CRF (SAEs, ADRs, Pregnancy information will be collected by using the SAE, ADR, Pregnancy Reporting Form).

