9. SUBJECT COMPLETION AND WITHDRAWAL

9.1. Subject completion

A subject who is available for the concluding follow-up contact 21 days after receiving *Fluarix Tetra* is considered to have completed the drug use investigation.

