9.2. Subject withdrawal

Subjects who are withdrawn because of SAEs/AEs must be clearly distinguished from subjects who are withdrawn for other reasons. Physicians will follow subjects who are withdrawn as result of a SAE/AE until resolution of the event (see Section 7.3).

Withdrawals will not be replaced.

From an analysis perspective, a 'withdrawal' from the drug use investigation refers to any subject who was not available for the concluding contact foreseen in the protocol.

All data collected until the date of withdrawal/last contact of the subject will be used for the analysis.

A subject is considered a 'withdrawal' from the drug use investigation when no study procedure has occurred, no follow-up has been performed and no further information has been collected for this subject from the date of withdrawal/last contact.

Physicians will make an attempt to contact those subjects who do not return for scheduled visits or follow-up.

Information relative to the withdrawal will be documented in the CRF. The physician will document whether the decision to withdraw a subject from the study was made by the

subject/subject's parent(s)/LAR(s) or by the physician, as well as which of the following possible reasons was responsible for withdrawal:

- SAE
- Non-SAE
- Protocol violation (specify)
- Consent withdrawal, not due to an AE
- Moved from the study area
- Lost to follow-up
- Death
- Other (specify)

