10.3.2. Total Safety cohort

The total Safety cohort will include all subjects who receive *Fluarix Tetra*, participated in the drug use investigation and provide post vaccination safety data.

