10.4. Conduct of analyses

Any deviation(s) or change(s) from the original statistical plan outlined in this protocol will be described and justified in the final report.

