10.5.2.1. Within group assessment

The AEs/***ADRs/SAEs*** will be analysed in the drug use investigation report according to the expectedness and unexpectedness criteria (Refer to ***GLOSSARY OF TERMS*** for the definitions of expected AEs and unexpected AEs).

The number and percentage, with exact 95% CI, of any AEs, ADRs ***and SAEs*** occurring within 21 days (Day 0 to Day 20) will be tabulated for the number of subjects receiving *Fluarix Tetra*.

The verbatim reports of signs and symptoms will be matched and coded according to the appropriate WHOART PT. The drug use investigation physician will review and confirm the appropriate WHOART PT by responding to data queries if any discrepancies are reported while coding. The percentage of subjects with AEs, ADRs, and ***SAEs*** occurring within 21 days (Day 0 to Day 20) with its exact 95% CI will be tabulated by PT.

The outcome of pregnancy (reported in the pregnancy report form) for subjects who were pregnant at the time of vaccination and those who become pregnant within 21 days after vaccination will be presented, if possible.

SAEs reported during the drug use investigation period [each subject receiving the vaccine up to 21 days (Day 0 to Day 20) after vaccination and for pregnant subjects until 6-8 weeks after delivery] will be described in detail, if possible.

The incidence proportion of AEs as overall and by age group and gender will be measured with the exact 95% CI. An exploratory comparison between these groups will be performed using Chi-square exact test with the statistical significance level 0.05.

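### Protocol 10.5.2 limits the safety analysis to subjects who completed 21-day follow-up; the cohort it names, and SAP 3.1, set no such condition

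*Protocol*

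**What the plan says.** **Rule with a completion condition.** Protocol 10.5.2 names the total safety cohort as the basis of the safety analysis. It then restricts that analysis to subjects vaccinated in line with the Korean prescribing information (PI) who "have completed 21-days follow-up after at least one dose, regardless of the number of dose".

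**Rules without one.**
- Protocol 10.3.2 defines the same cohort as vaccine recipients who "participated in the drug use investigation and provide post vaccination safety data".
- Protocol section 3 (and the synopsis) says that recipients of at least one dose who "can be evaluated for whether the subject experienced an AE will be included in the safety population".
- Protocol 9.2 treats a subject missed at the closing contact as a withdrawal, and adds: "All data collected until the date of withdrawal/last contact of the subject will be used for the analysis".
- SAP 3.1 repeats the substance of 10.3.2. Its item 4, labelled as follow-up failure, excludes a subject only when AE status is not known or is not entered in the CRF. SAP 6.3 runs the safety analysis on this set.

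**What completion means.** Protocol 9.1 gives it as follows: "A subject who is available for the concluding follow-up contact 21 days after receiving" the vaccine has completed. Section 3 adds: "Subjects for whom diary card transcription into CRF will be done through phone contact are considered to have completed the drug use investigation".

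**Which rule prevails.** Nothing says. Protocol 10.4 states only that departures from the "original statistical plan outlined in this protocol will be described and justified in the final report".

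**The concern.** The plan's only objective is safety, and one of its rules for the safety percentages selects on something that can follow from the outcome. Protocol 9.2 lists death and serious adverse event (SAE) among the reasons for withdrawal, so subjects can become non-completers because of the events being counted. Under 10.5.2 those subjects leave both numerator and denominator. Under 10.3.2, section 3 and SAP 3.1 they stay.

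The 9.2 commitment to use withdrawals' data cannot be met in the safety tables if 10.5.2 is applied as written. SAP 3.2 does not list non-completers, so they would not appear in the non-safety analysis set either. Two analysts working from the same documents could produce different AE percentages from the same data, and each could cite a section in support.

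**Working it through.** **1. Passages side by side.** Take a subject who receives one dose in the study, reports an AE on day 5 and is then lost, with no other exclusion applying.

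| Rule | In the safety percentages? |
|---|---|
| Protocol 10.3.2 | Yes: safety data were given |
| Protocol section 3 | Yes: AE occurrence can be judged |
| Protocol 9.2 | Data up to last contact are used |
| SAP 3.1 with item 4 | Yes: AE status is known |
| Protocol 10.5.2 | No: no completed 21-day period |

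The conflict is limited to subjects with no completed period after any dose. A two-dose child followed to the end after one dose meets 10.5.2. Protocol 10.4.1 also restricts the analysis to subjects whose conclusion page has arrived by the cut-off. As worded, that is a data cut-off; it neither requires completion nor ranks the definitions.

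**2. The plan's own intervals.** Table 4 gives exact (Clopper-Pearson) limits for n = 600:

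lower = Beta⁻¹(0.025; x, n − x + 1), upper = Beta⁻¹(0.975; x + 1, n − x).

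At 10%, x = 60 gives 7.72 to 12.68%, printed as 7.7 to 12.7. All eight rows reproduce to one decimal.

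**3. Inputs for the illustration.**
- From the plan: 720 enrolled per group and 20% dropout (protocol 10.2). Completers = 720 × 0.80 = 576; non-completers = 144.
- Assumed: the event counts below, and that all other non-completers have unknown AE status, so item 4 removes them.

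**4. Results.**

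| Assumed case | Protocol 10.5.2 | SAP 3.1 |
|---|---|---|
| One death before the concluding contact | 0/576 = 0% (0 to 0.64) | 1/(576 + 1) = 1/577 = 0.17% (0.00 to 0.96) |
| Same, with 5% non-completion (720 × 0.95 = 684) | 0/684 = 0% (0 to 0.54) | 1/685 = 0.15% (0.00 to 0.81) |
| 58 completers with an AE; 3 others report an AE, then are lost | 58/576 = 10.1% (7.7 to 12.8) | (58 + 3)/(576 + 3) = 61/579 = 10.5% (8.2 to 13.3) |

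With no events the upper limit is 1 − 0.025^(1/n); for n = 576 this is 0.64%.

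**5. Range.** The documents do not say how many non-completers will have known AE status. If none do, the two sets are identical. If a quarter do (36), and 20% of those had an AE (7 subjects), the SAP 3.1 figure is 65/612 = 10.6% (8.3 to 13.3). If half of the 36 had an AE (18), it is 76/612 = 12.4% (9.9 to 15.3). At the far end, with all 144 known and half with an AE (72), it is 130/720 = 18.1% (15.3 to 21.1). Nothing in the documents makes that last case likely.

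**The case against.** The strongest reply is that the working set is already settled. SAP V5.0 (2021) is later than protocol Amendment 3 (March 2019), defines its set in 3.1 and applies it in 6.3, and protocol 10.4 provides for departures. Follow-up is short and a phone contact counts as completion. Most subjects missed at the single follow-up contact after a dose would also have unknown AE status, so both rules drop them. SAEs are still reported to the sponsor and described in detail under 10.5.2.1.

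Most of this stands, and it is why the effect is small. It does not remove the conflict. The SAP does not record its set as a departure from 10.5.2, so nothing prompts the description that 10.4 calls for. No text places the SAP above the protocol.

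A reader might also infer more than the documents support:
- **A third denominator.** Protocol 10.5.2.1 says that results "will be tabulated for the number of subjects receiving" the vaccine, which could be taken as all 720. But it is a subsection of 10.5.2, which names the total safety cohort, and SAP 6.3 uses the safety analysis set. The natural reading is recipients within that cohort.
- **A death is certain to be dropped.** This is likely, because 9.2 lists death as a withdrawal reason. It is not certain. Completion turns on availability for a contact, parents are the persons contacted for children under 12, and no text says whether a parent's contact after a child's death counts.
- **Lost subjects will be counted as event-free.** Table 1 has AEs recorded at enrolment as well as at follow-up, so a no-AE entry that day might seem to settle status under item 4. The follow-up-failure label of item 4 points the other way. This is a separate drafting gap that the fix should close; it is not an effect of 10.5.2.

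**Conclusion.** The conflict is real and sits in current text: 10.5.2 is wrong as written, because it adds a condition that the cohort it names does not have, and that condition can remove subjects because of their outcome. Severity is minor. In the illustrations with one to three affected subjects, the tabulated result moves from no event to one (0% to 0.17%) or from 10.1% to 10.5%, with overlapping intervals.

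The sizes rest on assumed event counts, the plan's 20% dropout read as non-completion, and unknown AE status for all other non-completers. A larger shift would need many non-completers with known status and a clearly higher AE rate among them. What is affected is a tabulated percentage. The documents do not support a claim that serious events would go unreported.

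**What to change.** **Protocol 10.5.2 and 10.5.2.1.** Replace the completion condition with the 10.3.2 / SAP 3.1 rule: at least one in-study dose and AE status established. Keep the condition of vaccination in line with the PI. State that SAP 3.1 is the set used, including for the 10.5.2.1 tables.

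**SAP 3.1 item 4.** State that AE status is established by:
- any AE, SAE or death recorded at any time after vaccination, including at the vaccination visit; or
- for a subject without an AE, a follow-up contact or returned diary card after the day of vaccination.

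State that neither a withdrawal record without AE information (for example lost to follow-up, or moved away) nor a no-AE entry made only at the enrolment visit establishes it.

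**Protocol 10.4.1.** State that receipt of the conclusion page is a data cut-off that applies to withdrawn subjects too, and is not a completion requirement.

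**Sensitivity table.** Report the completer-only result by study group, with the number of non-completers with and without an AE.

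**Cost.** A few sentences in the protocol, which make an amendment subject to local submission rules (protocol 6.1), a short addition to the SAP, and one table. No new data are needed. Without an amendment, the SAP can state that its set is the one used, and the final report can describe and justify the departure under 10.4.

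**Downside.** Some subjects will have under 21 days of observation, and early losses known only because they reported an event can raise the proportion slightly. The completer-only table makes this visible.

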10.5.2.1. Within group assessment

The AEs/***ADRs/SAEs*** will be analysed in the drug use investigation report according to the expectedness and unexpectedness criteria (Refer to ***GLOSSARY OF TERMS*** for the definitions of expected AEs and unexpected AEs).

The number and percentage, with exact 95% CI, of any AEs, ADRs ***and SAEs*** occurring within 21 days (Day 0 to Day 20) will be tabulated for the number of subjects receiving *Fluarix Tetra*.

The verbatim reports of signs and symptoms will be matched and coded according to the appropriate WHOART PT. The drug use investigation physician will review and confirm the appropriate WHOART PT by responding to data queries if any discrepancies are reported while coding. The percentage of subjects with AEs, ADRs, and ***SAEs*** occurring within 21 days (Day 0 to Day 20) with its exact 95% CI will be tabulated by PT.

The outcome of pregnancy (reported in the pregnancy report form) for subjects who were pregnant at the time of vaccination and those who become pregnant within 21 days after vaccination will be presented, if possible.

SAEs reported during the drug use investigation period [each subject receiving the vaccine up to 21 days (Day 0 to Day 20) after vaccination and for pregnant subjects until 6-8 weeks after delivery] will be described in detail, if possible.

The incidence proportion of AEs as overall and by age group and gender will be measured with the exact 95% CI. An exploratory comparison between these groups will be performed using Chi-square exact test with the statistical significance level 0.05.

11. ADMINISTRATIVE MATTERS

To comply with acceptable ethical principles, local regulatory requirements, and administrative obligations relating to data collection, monitoring, archiving data, audits, confidentiality, and public disclosure must be fulfilled. Blinding of subjects initials when safety data is used for analysis and for GSK LOC provides the subject's No. on the PMS report before submission to MFDS. (GSK does not forward personally identifiable information and MFDS requires reporting of drug use investigation subject's No. in the PMS report).

11.1. Case Report Form

CRFs (and subject diary cards, if applicable), will be supplied by GSK Vaccines for recording all data.

Unless specifically required by MFDS, subject initials will not be collected nor transmitted to GSK. Subject data necessary for analysis and reporting will be entered/transmitted into a validated database or data system. Clinical data management will be performed in accordance with applicable data cleaning procedures.

While completed CRFs are reviewed by a GSK Vaccines' designated study monitor at the study site, omissions or inconsistencies detected by subsequent in-house CRF review may necessitate clarification or correction of data or omissions or inconsistencies with documentation and approval by the physician or appropriately qualified designee. In all cases the physician remains accountable for the study data collected.

Any questions or comments related to the CRF should be directed to the assigned study monitor.

The physician will keep a paper copy of each CRF and any data query forms of the final version of the data generated at the site.

11.2. Monitoring by GSK Vaccines

Monitoring visits by a GSK Vaccines' designated study monitor are for the purpose of confirming that GSK Vaccines' sponsored study are being conducted in accordance with the acceptable ethical principles and the regulatory requirement(s) (verifying continuing compliance with the protocol, amendment(s), verifying that the site staff and facilities continue to be adequate to conduct the study).

The physician must ensure provision of reasonable time, space, and qualified personnel for monitoring visits.

Direct access to all study-site related and source data is mandatory for the purpose of monitoring review. The monitor will perform a CRF review and a SDV. By SDV we understand verifying CRF by comparing them with the source data that will be made available by the physician for this purpose.

The Source Documentation Agreement Form describes the source data for the different data in the CRF. This document should be completed and signed by the study monitor and physician and should be filed in the monitor's and physician's study file. Any data item for which the CRF will serve as the source must be identified, agreed, and documented in the source documentation agreement form.

In accordance with applicable regulations, GSK monitors will contact the site prior to the start of the study to review with the site staff the protocol, study requirements, and their responsibilities to satisfy regulatory and ethical requirements. When reviewing data collection procedures, the discussion will also include identification, agreement, and documentation of data items for which the CRF entries will serve as the source document.

GSK will monitor the study to verify that, amongst others, the:

- Data are authentic, accurate, and complete.
- Safety and rights of subjects are being protected.
- Study is conducted in accordance with the currently approved protocol and any amendments, any other study agreements, acceptable ethical principles, applicable local regulatory requirements, and all applicable regulatory requirements.

The physician and the head of the medical institution (where applicable) agrees to allow the monitor direct access to all relevant documents.

Upon completion or premature discontinuation of the study, the monitor will conduct site closure activities with the physician or site staff, as appropriate, in accordance with applicable regulations.

11.3. Archiving of data at study sites

Following closure of the study, the physician must maintain all site study records in a safe and secure location. The records must be maintained to allow easy and timely retrieval, when needed (e.g. audit or inspection), and whenever feasible, to allow any subsequent review of data in conjunction with assessment of the facility, supporting systems, and staff. Where permitted by applicable laws/regulations or institutional policy, some or all of these records can be maintained in a validated format other than hard copy (e.g. microfiche, scanned, electronic for studies with an eCRF); however, caution needs to be exercised before such action is taken. The physician must assure that all reproductions are legible and are a true and accurate copy of the original and meet accessibility and retrieval standards, including re-generating a hard copy, if required. Furthermore, the physician must ensure there is an acceptable back-up of these reproductions and that an acceptable quality control process exists for making these reproductions.

GSK will inform the physician/institution of the time period for retaining these records to comply with all applicable regulatory requirements. However, the physician/institution should seek the written approval of the sponsor before proceeding with the disposal of these records. The minimum retention time will meet the strictest standard applicable to that site for the study, any institutional requirements or applicable laws or regulations; otherwise, the minimum retention period will default to 3 years.

The physician/institution must notify GSK of any changes in the archival arrangements, including, but not limited to, the following: archival at an off-site facility, transfer of ownership of the records in the event the physician leaves the site.

11.4. Audits

To ensure compliance with acceptable ethical principles and all applicable regulatory requirements, GSK may conduct a quality assurance audit. Regulatory agencies may also conduct a regulatory inspection of this study. Such audits/inspections can occur at any time during or after completion of the study. If an audit or inspection occurs, the physician and institution agree to allow the auditor/inspector direct access to all relevant documents and to allocate his/her time and the time of his/her staff to the auditor/inspector to discuss findings and any relevant issues.

11.5. Posting of information on public registers

Study information from this protocol will be posted on www.clinicaltrials.gov before enrolment of subjects begins.

11.6. Ownership, confidentiality, and publication

11.6.1. Ownership

All information provided by GSK and all data and information generated by the site as part of the study (other than a subject's medical records) are the sole property of GSK.

All rights, title, and interests in any inventions, know-how or other intellectual or industrial property rights which are conceived or reduced to practice by site staff during the course of or as a result of the study are the sole property of GSK, and are hereby assigned to GSK.

If a written contract for the conduct of the study which includes ownership provisions inconsistent with this statement is executed between GSK and the study site, that contract's ownership provisions shall apply rather than this statement.

